14. STATISTICS

This section outlines the planned statistical analyses. Additional details will be described in a separate statistical analysis plan (SAP).

14.1. Analysis Populations

Full Analysis Set: Part 1: All patients enrolled in the study and have received at least one dose of study drug; Part 2: All patients randomized in the study

Safety Population: All patients enrolled/randomized in the study who have received at least one dose of study drug (including placebo)

Per Protocol Set: All patients enrolled/randomized in the study, who have received at least one dose of study drug (including placebo) with no CSR-reportable protocol violations and at least one post-baseline MRI evaluation

Pharmacokinetic Population: All patients who have received at least one dose of study drug and have sufficient PK samples collected and assayed for PK analysis

14.2. Statistical Analysis Considerations

14.2.1. Patient Demographics and Disposition

Individual patient demographic data will be listed by patient.

Descriptive statistics (N, mean, SD, median, minimum, and maximum) will be provided for continuous demographic variables (age, weight, height, and BMI) and frequency counts will be tabulated for categorical demographic variables (sex, race, ethnicity) by treatment and overall for each study part (Part 1 and Part 2). Age will be calculated based on birth date and informed consent date.

Individual patient disposition data will be listed by patient.

Frequency counts will be tabulated for disposition data and will consist of the number of patients completing the study (Yes / No) along with frequency counts of primary reason for discontinuation (provided there is at least one patient who discontinued). Summaries will be provided by treatment and overall for each study part (Part 1 and Part 2).

14.2.2. Drug Exposure

Individual study drug administration data will be listed by patient. Descriptive statistics of study drug exposure will be presented.

14.2.3. Efficacy Data

Part 1

Individual efficacy data will be listed. For muscle strength (as assessed by handheld dynamometer), the MVIC value will be derived for each side and the average maximum peak force value [from the left and right sides] will be determined for each individual patient and scheduled time. For the MVIC value for each side treated as well as the average from the left and right sides, CMTES2 score, CMT-HI total score and selected subscale scores, and motor

Clinical Study Protocol Study A083-03 Revision: 03

function test assessments, raw and changes from baseline (percent and absolute change) for the injected muscle will be summarized for each scheduled time using descriptive statistics. For each efficacy variable, a repeated-measures ANCOVA model will be fitted and least square mean estimates of the effect of ACE-083 and the corresponding 90% confidence intervals will be provided for the percent change from baseline. For muscle strength parameters, the change from the screening to baseline value will serve as the control for each cohort and will be summarized together with post-baseline data. Baseline is defined as the last non-missing value prior to dosing. Theoretically, this should be the Day 1 predose value. Other strength measurements will be summarized and reported similarly. Additional analyses may be performed as appropriate.

Analyses described above concerning selected motor function test assessments related to gait will be considered as exploratory.

Part 2

Individual efficacy data will be listed. For muscle strength, the MVIC value and decimal MMT-MRC score will be derived for each side and the average [from the left and right sides] will be determined for each individual patient and scheduled time.

Double-blind, placebo-controlled phase

For the MVIC value and decimal MMT-MRC score for each side treated as well as the average from the left and right sides, CMTES2 score, CMT-HI total score and selected subscale scores, and motor function test assessments, raw data and changes from baseline (percent and absolute change) from baseline will be summarized by treatment for each scheduled time using descriptive statistics. In addition, a mixed model will be fitted to assess the treatment effect (ACE-083 vs. placebo) using a 2-sided 0.10 significance level for the percent change from baseline. Least squares estimates of the treatment effect and corresponding 90% confidence intervals will be provided. In addition, least squares estimates of the treatment effect and corresponding 90% confidence intervals will be provided for patients having dorsiflexion MMT-MRC grade of 4- to 4+ on both sides.

Additional analyses may be performed as appropriate.

Open-label extension

For the MVIC value and decimal MMT-MRC score for each side treated as well as the average from the left and right sides, CMTES2 score, CMT-HI total score and selected subscale scores, and motor function test assessments, raw data and changes (percent and absolute change) from the start of the open-label extension (Day 190) will be summarized by treatment for each scheduled time using descriptive statistics.

Additional analyses may be performed as appropriate.

Open-label extension vs. double-blind placebo-controlled phase

For the MVIC value [average from the left and right sides] decimal MMT-MRC score [average from the left and right sides], CMTES2 score, CMT-HI total score and selected subscale scores, and motor function test assessments, the effect of ACE-083 administered during the open-label extension compared to the treatment administered in the double-blind placebo-controlled phase will be examined for those receiving ACE-083 during the double-blind phase and separately for those receiving placebo during the double-blind phase by comparing the absolute and/or percent

ACE-083 **Clinical Study Protocol** Study A083-03 Revision: 03 changes [depending on the parameter] observed between Day 190 and pre-first treatment baseline (1st 6 months) and Day 358 versus Day 190 (2nd 6 months) using a mixed model. Least squares estimates of this effect and 95% confidence intervals will be provided. In addition, least squares estimates of this effect and corresponding 95% confidence intervals will be provided for patients having dorsiflexion MRC-MMT grade of 4- to 4+ on both sides.

Additional analyses may be performed as appropriate.

14.2.4. **Pharmacodynamic Data**

Part 1

Individual pharmacodynamic data will be listed. For individual pharmacodynamic data that is measured on the left and right side (i.e., MRI), the average of the left and right side assessments will also be listed and summarized.

Descriptive statistics (change from baseline [percent and absolute change]) will be provided by treatment group and scheduled time. In addition, for muscle volume and intramuscular fat fraction, a repeated measures ANCOVA will be fitted to the percent change from baseline data and estimates of the effect of ACE-083 at 3 weeks post last dose and corresponding 90% confidence intervals will be provided.

Additional analyses may be performed as appropriate.

Part 2

Individual pharmacodynamic data will be listed. For individual pharmacodynamic data that is measured on the right and left side (i.e., MRI), the average of the left and right side assessments will also be listed and summarized.

Double-blind, placebo-controlled phase

Descriptive statistics for raw data and changes from baseline (percent and/or absolute change) will be provided for each pharmacodynamic parameter by treatment group for each scheduled time. For pharmacodynamic parameters that are measured on the right and left side (i.e., MRI), the descriptive statistics will include summaries for each side and the average of the right and left sides.

The primary pharmacodynamic parameter will be the percent change in total muscle volume (average of left and right side) 3 weeks after the last dose of the double-blind treatment period (Day 190) from the corresponding baseline. A mixed model will be used to assess the treatment effect (ACE-083 vs. placebo) using a 2-sided, 0.10 significance level. If data from the end of treatment visit are missing, the last observation will be carried forward. Additional techniques for handling missing data will also be evaluated as sensitivity analyses to the last observation carried forward approach. Least squares estimates of the effect of ACE-083 and the corresponding 90% confidence interval will be produced. In addition, least squares estimates of the treatment effect and corresponding 90% confidence intervals will be provided for patients having dorsiflexion MRC-MMT grade of 4- to 4+ on both sides.

For each secondary pharmacodynamic parameter, a mixed model will also be used to assess the treatment effect using a 2-sided 0.10 significance level for the following secondary

09 January 2019 Acceleron Pharma Inc. Clinical Study Protocol Study A083-03 Revision: 03

pharmacodynamic variables: percent change from baseline for the average of the left and right side at 3 weeks after the last dose of the double-blind treatment period (Day 190) for intramuscular fat fraction as well as derived variables such as contractile muscle fraction and contractile muscle volume. Least squares estimates of the effect of ACE-083 and corresponding 90% confidence interval will be provided. In addition, least squares estimates of the treatment effect and corresponding 90% confidence intervals will be provided for patients having dorsiflexion MRC-MMT grade of 4- to 4+ on both sides.

For biomarker data (e.g., IGF-1 and CTX) and TA CMAP amplitude, raw data and changes from baseline (percent and absolute change) will be summarized by treatment group and scheduled time. Such analyses will be considered exploratory.

Additional analyses may be performed as appropriate.

Open-label extension

Descriptive statistics for the percent change from baseline will be provided for each pharmacodynamic variable by treatment group for each scheduled time. For pharmacodynamic variables that are measured on the right and left side (i.e., MRI), the descriptive statistics will include summaries for each side and the average of the right and left sides.

For each pharmacodynamic variable, raw data and changes (percent and/or absolute change) from the start of the open-label extension (Day 190) will be summarized by treatment for each scheduled time using descriptive statistics.

Additional analyses may be performed as appropriate.

Open-label extension vs. double-blind placebo-controlled phase

For each of the following pharmacodynamic variables, a mixed model will be used to assess the effect ACE-083 administered during the open-label extension [Day 358 vs. Day 190 (2nd 6 months)] compared to the effect of the treatment administered in the double-blind placebo-controlled phase [Day 190 vs. pre-first treatment baseline (1st 6 months)] separately for those receiving placebo during the double-blind phase as well as for those receiving ACE-083 during the double-blind phase:

- Percent change in total muscle volume (average of right and left sides) during the openlabel extension vs. double-blind phase
- Percent change in intramuscular fat fraction (average of right and left sides) during the open-label extension vs. double-blind phase
- Percent change in contractile muscle fraction (average of right and left sides) during the open-label extension vs. double-blind phase
- Percent change in contractile muscle volume (average of right and left sides) during the open-label extension vs. double-blind phase

Least squares estimates of this effect and 95% confidence intervals will be provided. In addition, point estimates of this effect and corresponding 95% confidence intervals will be provided for patients having dorsiflexion MRC-MMT grade of 4- to 4+ on both sides.

Additional analyses may be performed as appropriate.

Clinical Study Protocol Study A083-03 Revision: 03 14.2.4.1. Pooled Analyses

If applicable, similar analyses will be performed for pooled Part 1 and 2 data for patients at the same dose level. Pooling by the estimated local dose of ACE-083 in the injected muscle (i.e., mg ACE-083/g muscle) may also be performed. Details of these analyses will be included in the SAP.

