8. STUDY POPULATION

8.1. Inclusion Criteria

Patients are eligible to be included in the study only if they meet all of the following criteria at screening:

Inclusion Criteria:

- 1. Age ≥ 18 years
- 2. Diagnosis of CMT1 or CMTX confirmed by:
 - a. Clinical presentation and electrodiagnostics
 - b. Genetically confirmed CMT1 or CMTX (Appendix 3) for the patient or first-degree relative
- 3. Part 1:
 - a. Six-minute walk distance (6MWD) of at least 150 meters (without a brace or walker)
 - b. Independent ambulation for at least 10 meters, without a brace
 - c. Left and right ankle plantar flexion MRC grade 4+ to 5, inclusive

Part 2:

- a. $6MWD \ge 150$ and ≤ 500 meters (without a brace or walker); a maximum of 20% of enrolled patients with $6MWD \ge 450$ meters will be included
- b. Left and right ankle plantar flexion MRC grade 4- to 5, inclusive
- 4. Left and right ankle dorsiflexion Medical Research Council (MRC) manual muscle testing (MMT) grade 3 to 4+ inclusive (Appendix 4). No more than 12 of the 40 subjects may have a grade of 3 or 3+ on one or both sides.
- 5. Females of childbearing potential (defined as sexually mature women who have not undergone hysterectomy or bilateral oophorectomy, or are not naturally postmenopausal ≥ 24 consecutive months) must have negative urine pregnancy test prior to enrollment and use highly effective birth control methods (abstinence, oral contraceptives, barrier method with spermicide, or surgical sterilization) during study participation and for 8 weeks following the last dose of ACE-083. Hormonal birth control use must be stable for at least 14 days prior to Day 1. Males must agree to use a condom during any sexual contact with females of childbearing potential while participating in the study and for 8 weeks following the last dose of ACE-083, even if he has undergone a successful vasectomy. Patients must be counseled concerning measures to be used to prevent pregnancy prior to the first dose of ACE-083.
- 6. Ability to adhere to the study visit schedule/procedures, and to understand and comply with protocol requirements
- 7. Signed written informed consent

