14.3. Determination of Sample Size

There is no formal sample size calculation for Part 1. Six patients in each cohort will provide sufficient data to evaluate safety and preliminary efficacy data.

The sample size calculation for Part 2 is based upon the expected percent change from baseline in total muscle volume of the injected TA 3 weeks after the last dose. A 10% difference between ACE-083-treated and placebo groups in the percent change in total muscle volume from baseline is considered to be clinically meaningful. The SD is estimated to be approximately 10% for each group based on preliminary MRI data for the ACE-083 treated side of the TA muscle from Part 1 of the Phase 2 study in FSHD patients. Assuming a 2-sided type 1 error rate of 0.10, a 10% difference in percent change from baseline between the ACE-083-treated and placebo groups in total muscle volume, a standard deviation of 10% for each group, and a 1:1 randomization, 90% power is achieved with a total sample size of n=36 patients (18 active, 18 placebo), based on a standard t-test. Clinical Study Protocol Study A083-03 Revision: 03 In addition, this sample

In addition, this sample size provides 90% power to detect a 10% difference in 6MWD, based on an assumed estimated SD of 10% (based off of available data from Part 1 of the Phase 2 study in FSHD patients as well as data from Part 1 of this study, 3-weeks post last dose) and a 2-sided type 1 error rate of 0.10.

In order to account for dropouts (up to 10%), 40 patients will be randomized to study treatment (20 active, 20 placebo) to ensure that at least 18 patients per treatment group complete the double-blind treatment period.

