## **4.9. Subgroup Analyses**

Subgroup analyses will be performed for selected efficacy and pharmacodynamics data from the double-blind period of Part 2.

Subgroups consist of the following:

- Ankle Dorsiflexion MRC-MMT Grade {weaker of two sides at Screening}: (3 to 4-; 4 to 4+)
- Ankle Dorsiflexion Screening MRC-MMT Grade of 4- to 4+ on both left and right sides
- Plantar Flexion MRC-MMT Grade {weaker of two sides at Screening}: (4- to 4+; 5- to 5)
- Knee Extension MRC-MMT Grade {weaker of two sides at Screening}: (3+ to 4+; 5- to 5)
- MRC-MMT Grade {weaker of two sides at Screening} for plantar flexion and knee extension
  - Levels are “Both 5- to 5” and “Not both 5- to 5”.
  - “Both 5- to 5” means that the MRC-MMT grade {weaker of two sides} for both plantar flexion and knee extension must both be between 5- and 5.

- “Not both 5- to 5+” means that the MRC-MMT grade {weaker of two sides} for any or both plantar flexion and knee extension should not both be between 5- and 5+. For example, a patient with plantar flexion MRC-MMT grade {weaker of two sides} of a 5- and knee extension MRC-MMT grade {weaker of two sides} of 4 would be classified as “Not both 5- to 5+”.
- Baseline Fat Fraction (%): (< median;  $\geq$  median)
- CMT type: (CMT1, CMTX)
- CMT gene mutation: (CMT1A, not CMT1A)
- Usage of Braces (Yes; No)
  - This information is contained in the individual patient’s CMT disease history
- Dose per Calculated Contractile Muscle Mass (mg/g): (< median;  $\geq$  median)
- Exercise Program: (resistance; no resistance)
  - The “resistance” subgroup includes patients who responded “Yes” to the question “Does the patient have a regular (at least once a week) exercise program?” and reported “Resistance training” as a type of exercise program.
  - The “no resistance” subgroup includes patients who responded “Yes” to the question “Does the patient have a regular (at least once a week) exercise program?” and did not report “Resistance training” as a type of exercise program.
- Baseline CMT-HI Total Score: (< median;  $\geq$  median)
- Activity level (steps/d): (< median;  $\geq$  median)
  - This is defined as the average number of steps per day as measured by the PAMSys™ device over the patient’s study participation in the Part 2 double-blind period, adjusted for overall compliance in using the device to record such activity.
- ADA (ADA +; ADA-)

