  - ADA+ means that the patient had positive ADA for ACE-083 at least once during the double-blind period of Part 2
  - ADA- means that the patient did not have positive ADA for ACE-083 at least once during the double-blind period of Part 2

Subgroup analyses will be performed for the following parameters:

- Day 190 average percent change in total muscle volume from baseline
- Day 190 average percent change in calculated contractile muscle volume from baseline
- Day 190 average absolute change in fat fraction from baseline
- Day 190 average percent change in fat fraction from baseline
- Day 190 average percent change in ankle dorsiflexion MVIC from baseline

- Day 190 average absolute change in ankle dorsiflexion MMT-MRC decimal score from baseline
- Day 190 percent change in 6MWD from baseline
- Day 190 percent change in time to complete 10mW/R from baseline
- Day 190 absolute change in CMT-HI total score from baseline
- Day 190 absolute change in CMT-HI foot/ankle strength subscale score from baseline
- Day 190 absolute change in CMT-HI balance subscale score from baseline
- Day 190 absolute change in CMT-HI fatigue subscale score from baseline
- Day 190 absolute change in CMT-HI mobility subscale score from baseline
- Day 190 absolute change in CMT-HI activities subscale score from baseline
- Fall risk reduction during double-blind period

Subgroup analyses will be performed using similar ANCOVA models described in previous sections for each subgroup category provided that the sample size is at least 4. Because of the reduced sample size within each subgroup category, it is not planned to include CMT-TYPE into such models. For each subgroup category, the treatment effect will be estimated and tested using a 0.1 (two-sided) significance level with the corresponding 90% confidence interval. Bar charts of the least squares mean estimates ( $\pm$  SEM) for each of the treatment groups will be provided.

For purposes of this study, findings of subgroup analyses are considered to yield hypothesis generating statements for future study. It is not planned to control the overall type-1 error.

Additional analyses may be performed as appropriate.

Data from multiple imputations described in [Section 4.7.2.2.1](#) will be used.

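### SAP 4.9 omits some of the estimates the protocol promises for patients graded 4- to 4+ on both sides, without declaring it, and drops CMT-TYPE from that subset's models for a reason that fits it poorly

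*Protocol*

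**What the plan says.** In Part 2 the protocol gives separate estimates for one dorsiflexion subset, in five places. For the double-blind efficacy variables in 14.2.3 (MVIC, MMT score, CMTES2, CMT-HI, motor function tests), least squares estimates with 90% intervals "will be provided for patients having dorsiflexion MMT-MRC grade of 4- to 4+ on both sides". Section 14.2.4 repeats this for the primary endpoint and for the secondary pharmacodynamic variables, which include contractile muscle fraction: the estimates and intervals "will be provided for patients having dorsiflexion MRC-MMT grade of 4- to 4+ on both sides". For the open-label versus double-blind comparisons, 14.2.3 promises subset least squares estimates for efficacy, and 14.2.4 promises "point estimates of this effect and corresponding 95% confidence intervals" for the pharmacodynamic variables.

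SAP 4.9 lists the same subset as one of 14 subgroup factors. Its scope is: "Subgroup analyses will be performed for selected efficacy and pharmacodynamics data from the double-blind period of Part 2". On the model it says: "Because of the reduced sample size within each subgroup category, it is not planned to include CMT-TYPE into such models". Subgroup categories are analysed down to a size of 4, and findings are labelled hypothesis generating.

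The size of the subset is governed by Protocol 8.1, criterion 4, which admits grades 3 to 4+ and adds: "No more than 12 of the 40 subjects may have a grade of 3 or 3+ on one or both sides".

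Protocol 14.5 commits the SAP to indicating deviations from the protocol's analyses. SAP Section 5 lists five modifications; none concerns this subset.

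**The concern.** There are two separate issues.

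The first is completeness. Results that the protocol promised beside the main analysis are absent from the SAP, and the section meant to record such changes is silent. If they are produced later, they will look post hoc; if not, a prespecified result has gone without notice.

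The second is the model. CMT type is the only stratification factor (Protocol 10.5, SAP 3.2) and is a covariate in the SAP's primary ANCOVA (4.8.2.2.1). Randomisation is not stratified by MMT grade, so CMT type may be unbalanced between arms inside the subset by chance. A rule written for subgroups as small as 4 removes the covariate from a subset that holds most of the trial. At stake is some precision and protection against that imbalance.

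**Working it through.** **Step 1: promised against planned.**

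| Subset estimate promised (protocol) | Planned in the SAP? |
|---|---|
| Total muscle volume, primary (14.2.4) | Yes, 4.9 |
| Fat fraction; contractile muscle volume (14.2.4) | Yes, 4.9 (calculated contractile volume) |
| Contractile muscle fraction (14.2.4) | No |
| MVIC, MMT score, 6MWD, 10-meter walk/run, CMT-HI (14.2.3) | Yes, 4.9 (CMT-HI total and five subscales) |
| CMTES2 (14.2.3) | No |
| Berg, a motor function test under 12.4 (14.2.3) | No |
| Open-label vs double-blind, efficacy (14.2.3) | No; 4.9 is double-blind only and 4.7.2.2.3 has no subset analysis |
| Open-label vs double-blind, pharmacodynamic (14.2.4) | No; same limit, and none in 4.8.2.2.3 |

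Contractile muscle fraction is defined in SAP 4.8.1.1 as 100 minus fat fraction, so its absolute change can be recovered from fat fraction. The promised percent change cannot. The SAP does not model it in the full set either. Section 5 does record the move from 95% to 90% intervals for the open-label versus double-blind comparisons, so changes of this kind were meant to be listed there.

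**Step 2: the plan's sample size.** Inputs from Protocol 14.3: two-sided alpha 0.10, difference 10, SD 10, power 90%. Per arm, n = 2(1.645 + 1.282)² × 10²/10² = 17.1, rounded up to 18. Noncentral-t power at 18 per arm is 90.2%. With 10% dropout, 36/0.90 = 40. The stated figures reproduce.

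**Step 3: size of the subset.** Within the eligible range of 3 to 4+, a patient without grade 3 or 3+ on either side is 4- to 4+ on both. Minimum at full enrolment: 40 − 12 = 28 (70%). If all four allowed dropouts fell in the subset, 24 would complete.

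**Step 4: cost of one degree of freedom.** With 28 patients, TREATMENT and BASELINE leave 25 residual df; adding CMT-TYPE leaves 24. The 90% multiplier goes from 1.708 to 1.711 (+0.16%). At 14 per arm the half-width goes from 1.708 × 10 × √(2/14) = 6.46 to 6.47 points. Power is 82.3% in both cases.

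**Step 5: allowing for chance imbalance.** I simulated stratified 1:1 allocation of 40 patients, a random 28 in the subset, 9 of 40 CMTX (22%, assumed), a true effect of 10, and total SD held at the protocol's 10. The difference between CMT types is assumed throughout.

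| Type difference | Mean 90% CI width without CMT-TYPE | With | Change | Power without / with |
|---|---|---|---|---|
| 0 | 13.1 | 13.2 | about +1% | 80% / 79% |
| 5 points | 13.2 | 13.0 | about −1% | 80% / 81% |
| 10 points | 13.2 | 12.0 | about −8 to −9% | 82% / 86% |

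Hand check at 10 points: between-type variance is 0.225 × 0.775 × 100 = 17.4, residual SD is √82.6 = 9.09, and 0.909 × 1.01 = 0.918, or about 8% narrower. At 5 points: 0.225 × 0.775 × 25 = 4.4, √95.6 = 9.78, and 0.978 × 1.01 = 0.988, or about 1% narrower. The mean treatment estimate was 10.0 with and without the term in every scenario.

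With 4 of 40 CMTX, the gain at 10 points falls to about 4%, and about 16% of trials leave at least one arm of the subset without a CMTX patient. With 9 of 40 this happens in under 1%.

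**The case against.** The SAP has good answers to several stronger readings.

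- *A reader might infer that dropping CMT-TYPE is an undeclared protocol deviation.* It is not. The protocol names no covariates for its mixed model, and SAP 4.9 states the drop and gives a reason. Only the missing estimates are undeclared.
- *A reader might infer that the hypothesis-generating label contradicts the protocol.* It does not. The protocol promises estimates and intervals in this subset, with no alpha, hierarchy or power attached.
- *A reader might infer that subset and full-set estimates cannot be compared.* For the linear models, omitting a covariate that is independent of randomised treatment leaves the target unchanged; only precision and chance imbalance are affected. The falls hazard ratio is a possible exception.
- *A reader might take 28 as a floor for the analysed set.* Enrolment is up to 40, and the SAP's primary population is the Per Protocol Set (4.2), so the number can be lower. Dropout alone need not reduce it, because SAP 4.9 uses the multiply imputed data.
- *Small numbers could mean sparse CMTX cells.* This stands in part. The 22% share is an assumption. Protocol 5.2 gives 40% for CMT1A alone and 10 to 15% for X-linked disease; other CMT1 types would lower the CMTX share. The remedy therefore needs a fallback.

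Most of the promised double-blind output survives, including the primary endpoint.

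**Conclusion.** The omission is established from the text alone. Subset estimates for CMTES2, Berg and contractile muscle fraction, and every open-label versus double-blind subset estimate, are promised in the protocol, absent from the SAP and not listed in Section 5.

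The CMT-TYPE point is a cheap improvement, not an error. The small-numbers reason suits a subgroup of 4 better than one of at least 28 at full enrolment. Keeping the term costs about 1% in interval width if CMT type is not prognostic and gains about 1% if the types differ by 5 points. The gain of 8 to 9%, with power of 86% instead of 82%, needs a 10-point difference, for which the documents give no support.

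A reader might go further and infer a fall to 70% power. That needs a 15-point difference added on top of the protocol's SD, making the total SD √(100 + 0.225 × 0.775 × 225) = 11.8. Neither is supported by the documents.

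**What to change.** 1. In SAP 4.9, exempt the subset graded 4- to 4+ on both sides from the reduced-model rule. Fit each endpoint's full-set ANCOVA, including CMT-TYPE, and revert to the reduced model only if an arm of the subset has no CMTX patient.
2. Add subset estimates for CMTES2, Berg, contractile muscle fraction and the open-label versus double-blind comparisons. Contractile muscle fraction has no full-set model in the SAP, so specify one; TREATMENT, BASELINE and CMT-TYPE, as for the other MRI variables, would serve for the double-blind analysis. The 90% intervals already declared in Section 5 can apply to the open-label comparisons.
3. If any of these are not wanted, list the omission in Section 5.

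The cost is SAP wording and a few more model runs on data already collected, plus about 1% in interval width if CMT type turns out not to matter.
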